16.2.3.4. Analysis of Change in 8-point SMBG profile from baseline

8-point SMBG profile at a visit will be calculated using available pre-visit measurements in the diary (performed in the week preceding the visit).

Descriptive statistics will be presented for the actual and change from baseline to scheduled visits for SMBG profile.

Treatment group comparison will be done using the same MMRM model as the primary efficacy analysis (without imputing missing values). Estimates of the means, LSMeans (2-sided 95% CIs) as well as treatment difference at each visit will be presented.

For graphical display at scheduled visits the mean and SD plot will be prepared for the actual Overall SMBG average measurement by visit, LSMeans and 95% CI from the same MMRM model will similarly be displayed graphically.

16.2.4. SUBGROUP ANALYSIS

The effect of subgroups mentioned in [section 8.6](#) on the change from baseline HbA1c at week 18 will be examined by employing a MMRM model. The subgroups will be included in the model along with the treatment group. Additionally separate subgroup analysis within each subgroup mentioned in [section 8.6](#) will be performed same MMRM model for treatment comparison within each subgroups.

The similar subgroups will also be examined for the immunogenicity parameters for the percent binding and the incidence analysis of cross reactive antibody. Besides examine subgroup by treatment interaction for percent binding. Separate analysis for both percent binding and incidence will be performed for treatment comparison within each subgroup.

Document:	\sasdata\Mylan\Insulin_glargine\SYA22825\Biostatistics\Documentation\SAP\MYL-1501D-3004_SAP_Final_2_0_clean.doc		
Author:	[name]	Version Number:	2.0
		Version Date:	18OCT2018
Template No:	CS_TP_BS016 Revision 4	Reference:	CS_WI_BS005
Effective Date:	01Apr2016		

16.3. EXPLORATORY PK ANALYSIS

Exploratory PK analysis will be performed by Mylan PK/DM department.

Descriptive statistics of PK concentration values will be presented for each scheduled visits by treatment group.

Treatment group comparison will be done using the GLM model on log-transformed PK concentration values including treatment, visit, treatment-by-visit interaction, time of administration of glargine [morning and evening], all as fixed effects. If treatment-by-visit interaction is not significant, this term will be dropped from the model, the reduced model will be performed to produce the final analysis. If treatment-by-visit interaction is significant, then this interaction term and visit term will be drop from the model and final model will be performed by visit with only treatment and time of administration in the model.

LSMeans for each treatment group and Geometric Mean Ratio between the treatment groups will be calculated. 2-sided 90% confidence intervals for the log transformed treatment difference and p-values will be provided.

The PK data will not be available at the time of database lock for the analysis. However the treatment will remain blinded during the laboratory assay. These data will be locked later and statistical analysis will be performed according to pre-specified method in this SAP

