6.3 Treatment phase

6.3.1 Visit 6 (Week 0)

After completion of the run-in phase without any major violation of the selection criteria the subjects will enter the randomized study treatment phase. During this visit the following procedures and assessments will be performed:

- Check selection criteria suitability
- Discuss and check compliance to standard of care specifics as per ADA 2017 guidelines, self-management of diabetes and life-style modifications with the subject
- Record body weight and calculate BMI
- Record concomitant medications since previous visit
- Record vital signs (sitting after 5 minutes rest; pulse, blood pressure, temperature and respiratory rate)
- Perform and document physical examination
- Perform 12-lead ECG (supine, after 5 minutes rest) and document results
- Record AEs, SAEs, local and systemic allergic reactions and hypoglycemic events since the previous visit
- Record device safety information
- Collect blood and urine samples for the following laboratory assessments:
 - Serum and urine pregnancy test for women of childbearing potential (only a negative urine test result is needed for dispensing drug)
 - Fasting plasma glucose
 - HbA1c
 - Hematology
 - Blood chemistry
 - Urine analysis
 - Fasting lipid profile
 - Immunogenicity analysis (collect blood sample prior to study drug administration)
 - PK analysis (collect blood sample prior to study drug administration)

- Review the results of 8-point SMBG measurements, performed on 3 days during the week
- Review current dosing of Lantus and Humalog and if necessary provide new dosing instructions and document the new dose and reason for change
- Dispense study medication MYL-1501D (product from Process VI or Process V), and Humalog
- Perform drug accountability and check for treatment compliance
- Review subject diary and provide information regarding the completion requirements and necessary glucose measurements provided.
- Perform randomization and document result

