7.2. BASELINE

Unless otherwise specified, baseline is defined as the last non-missing measurement taken prior to receiving randomized treatment reference (day of randomization) start date (including unscheduled assessments). In the case where the last non-missing measurement and the randomized treatment start date coincide, that measurement will be considered pre-baseline, but Adverse Events (AEs) and medications commencing on the randomized treatment start date will be considered post-baseline.

For insulin (mealtime, basal and total) levels, baseline is the value collected at Visit 6 (Week 0) which correspond to values collected prior injection of study medication.

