7.5. STATISTICAL TESTS

The default significant level will be (5%); confidence intervals will be 95% and all tests will be two-sided, unless otherwise specified in the description of the analyses.

Non-inferiority will be tested at 2.5% (one-sided) level of significance.

Document: \sasdata\Mylan\Insulin_glargine\SYA22825\Biostatistics\Documentation\SAP\MYL-1501D-3004_SAP_Final_2_0_clean.doc

Author: [name]

Version Number:

2.0

Version Date:

18OCT2018

Template No: CS_TP_BS016 Revision 4
Effective Date: 01Apr2016

Reference: CS_WI_BS005

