proc mixed data = datmichg method = REML order=internal;
  by _imputation_;
  class trtp(ref="Process V") strata sitegr1 avisit usubjid;
  model change = HbA1c_BASE trtp strata avisit sitegr1 trtp*avisit / DDFM =
  KR;
  repeated avisit / type = UN subject = usubjid;
  lsmeans trtp*avisit /diff cl;
  ods output diff = lsdiffs(where=(trt= 'Process IV' and _trt='Process V' and
  visit=_visit));
run;
```

```
/* Combine LSmean Differences for Visit 'Week 12' */
proc mianalyze parms(classvar = full) = lsdiffs (where = (visit = 'Week 12'));
  class trtp*avisit;
  modeleffects trtp*pvisit;
run;
```

```
/* Combine LSmean Differences for Visit 'Week 18' */
proc mianalyze parms(classvar = full) = lsdiffs (where = (visit = 'Week 18'));
  class trtp*avisit;
  modeleffects trtp*avisit;
run;
```

Note to programmers: In case of non-convergence or non-estimability issues for the generation of enough data to produce a monotone missing data pattern, replace the two proc mi by the following:

```
proc mi data = impute3 out = datamono seed =20171220 NIMPUTE=100
  round = 1 1 1 1 1 1 1 1 1 1 1 1 1 1 1 1 1 1 1 1
  min   = 0 0 0 0 0 0 0 0 0 0 0 0 0 0 0 0 0 0 0 0
  max   = 1 1 1 1 1 1 1 1 1 1 1 1 1 1 1 1 1 1 1 1;
  var trtpn  binstime inv01 inv02 inv03 inv04 inv05 inv06 inv07 inv08 inv09
inv10 inv11 inv12 inv13 HbA1c_BASE HbA1c_WK12 HbA1c_WK18;
  mcmc impute = monotone chain= multiple /*prior=ridge=p*/;
run;
```

Document:	\sasdata\Mylan\Insulin_glargine\SYA22825\Biostatistics\Documentation\SAP\MYL-1501D-3004_SAP_Final_2_0 clean.doc		
Author:	[name]	Version Number:	2.0
		Version Date:	18OCT2018
Template No:	CS_TP_BS016 Revision 4	Reference:	CS_WI_BS005
Effective Date:	01Apr2016		

Analysis Plan Template

```
proc mi data = datamono seed = 171016 out = datami NIMPUTE = 1;
  by _imputation_;
  class trtp strata sitegr1;
  var trtp strata sitegr1 HbA1c_BASE HbA1c_WK12 HbA1c_WK18;
  monotone regression;
run;
```

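### The exploratory PK model has no subject term or within-subject covariance, so its pooled 90% CI for the Process VI/V ratio is too narrow if a subject's samples correlate positively

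*SAP*

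**What the plan says.** SAP V2.0 section 16.3 (Exploratory PK Analysis) specifies a GLM on log concentration with "treatment, visit, treatment-by-visit interaction, time of administration of glargine [morning and evening], all as fixed effects". The interaction test then chooses between two routes.

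- If it is not significant, "this term will be dropped from the model, the reduced model will be performed to produce the final analysis".
- If it is significant, the "final model will be performed by visit with only treatment and time of administration in the model".

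The reported results are LS means, the geometric mean ratio, and "2-sided 90% confidence intervals for the log transformed treatment difference and p-values will be provided". The section also commits the PK analysis, which is run after a later lock, to the method written in the SAP. SAP V1.0 section 16.3 has the same model, and Protocol V2.0 gives no PK model.

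The schedule of events takes PK samples at Visits 6, 8, 10, 12 and 14 (Weeks 0, 2, 6, 12 and 18).

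The SAP's other repeated measurements are handled differently. The primary model in 16.1.3 uses an unstructured covariance, coded in Appendix 3 as "repeated avisit / type = UN subject = usubjid". The same MMRM, or a subject random effect, is specified for HbA1c by visit, fasting glucose, insulin dose, SMBG, laboratory values, vital signs, antibody binding and hypoglycemia rate.

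**The concern.** A subject stays in one arm throughout, so the treatment contrast is between subjects. Its precision depends mainly on the number of subjects and the spread of subject means. A fixed-effects model without a subject term instead counts about 4 × 202 = 808 values as independent. If samples from one person resemble each other, the treatment standard error is understated and the ratio's interval and p-value look more precise than the data allow.

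The omission has the opposite effect on the interaction test, which is a within-subject comparison. Its error term wrongly includes between-subject variation, so the test is conservative. When there is little or no true interaction, this steers the analysis towards the pooled model, which is the affected one.

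A separate, smaller gap is that 16.3 does not say whether Visit 6 is a response or the baseline. That sample is pre-dose, after Lantus run-in in both arms.

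**Working it through.** **Inputs from the documents.** 202 subjects randomized 1:1 (Protocol V2.0 section 7.1), so 101 per arm. Post-baseline PK samples per subject m = 4, or 5 with Visit 6. Two-sided 90% CI (16.3). Default test level 5% (SAP 7.5), taken to apply to the interaction test.

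**Assumed.** The within-subject correlation ρ of log concentration is not given. The range is 0.1 / 0.3 / 0.5 / 0.7, equal between all visits (compound symmetry), with complete data.

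**Step 1: standard error.** With total variance σ², the GLM takes the variance of a subject's mean as σ²/m. The correct value is σ²[1 + (m−1)ρ]/m. The understatement is therefore governed by D = 1 + (m−1)ρ, and the GLM interval has 1/√D of the correct width. N cancels.

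**Step 2: stated level.** True coverage of the nominal 90% CI is 2Φ(1.645/√D) − 1. At ρ = 0, D = 1 and this gives 90.0%. Simulation with 101 per arm (4,000 trials) gave 89.8% for m = 4. The stated level therefore reproduces only under independence.

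**Step 3: positive correlation, m = 4.** The true rejection rate of a nominal 5% test with no treatment difference is 2[1 − Φ(1.96/√D)].

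| ρ | D | Width ÷ correct width | Coverage of 90% CI | Rejection at nominal 5% |
|---|---|---|---|---|
| 0.1 | 1.3 | 0.877 | 85.1% | 8.6% |
| 0.3 | 1.9 | 0.725 | 76.7% | 15.5% |
| 0.5 | 2.5 | 0.632 | 70.2% | 21.5% |
| 0.7 | 3.1 | 0.568 | 65.0% | 26.6% |

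Worked line for ρ = 0.5: D = 1 + 3 × 0.5 = 2.5; √D = 1.581; 1.645/1.581 = 1.040; 2Φ(1.040) − 1 = 70.2%.

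In 6,000 simulated trials per setting, with a balanced morning/evening factor, coverage was 85 / 76 / 70 / 65% and the rejection rate 9 / 16 / 21 / 26%. In the same trials an analysis of subject means, which for balanced data equals a compound-symmetric mixed model, covered 89.8 to 90.5%.

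**Step 4: interaction test.** With no true interaction, the GLM's F statistic is deflated by about (1 − ρ). The simulated rejection rate of the nominal 5% test was 3.6 / 1.1 / 0.2 / 0.0%. The pooled model would then be reported in nearly every trial.

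**Step 5: Visit 6 as a fifth response.** With m = 5 the coverage formula gives 83.6 / 73.3 / 65.8 / 60.1%. A constant post-baseline difference d is also averaged with a zero at Visit 6, giving (4d + 0)/5 = 0.8d, a 20% shrinkage. In 1,500 simulated trials per setting, the interaction test diverted the analysis to the by-visit models in 10 / 6 / 2 / 0.2% of trials for d = 0.2 SD, but in about 67 to 70% for d = 0.5 SD. The dilution therefore matters mainly for small differences.

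**The case against.** **The wording may only be incomplete.** The statement that terms are fixed applies to the four terms listed, and a repeated-measures covariance is not a fixed effect. The SAP gives no PK code. Its text and code also differ elsewhere: 16.1.3 mentions subjects as a random effect, while the V2.0 Appendix 3 code has only a repeated statement. An analyst could therefore add the covariance. That is possible, but 16.3 ties the later analysis to the method written in the SAP. Where a subject effect was wanted, in 16.2.3.1 and 16.2.3.2, the SAP names it.

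**The size rests on assumptions.** This stands. If correlation decays from visit to visit, with ρ the adjacent-visit value (AR(1)), then D = 1 + (3ρ + 2ρ² + ρ³)/2 for m = 4. That gives 1.16 / 1.55 / 2.06 / 2.71, widths of 93 / 80 / 70 / 61% and coverage of 87 / 81 / 75 / 68%. Sampling is only preferably before the daily dose, so varying time since dose could lower ρ further. The shortfall shrinks, but its direction is the same for any positive ρ.

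**Little depends on it.** This also stands. PK is not an objective or endpoint in the protocol, no acceptance range is set, and descriptive statistics by visit are shown whichever model is used. That limits the severity but does not make the interval right.

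**Visit 6 is evidently the baseline.** SAP 7.2 supports this: "baseline is defined as the last non-missing measurement taken prior to receiving randomized treatment". Only a clarifying phrase is needed, and the main point holds with m = 4 or m = 5.

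**Conclusion.** The concern holds. Fitted as written, the pooled PK model gives a 90% CI that is too narrow and a p-value that is too small for any positive within-subject correlation. The effect is mild at a correlation of 0.1 (coverage about 85%) and large from about 0.3 (about 77% or lower with equal correlation, 81% or lower with AR(1) decay). These figures assume complete data and a correlation the documents do not supply; only the direction is certain. The by-visit models use one value per subject and are unaffected. Severity is minor, because the analysis is exploratory and the primary HbA1c conclusion does not depend on it.

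**What to change.** In SAP 16.3, replace the GLM with a mixed model on log concentration at Visits 8, 10, 12 and 14. Fixed effects are treatment, visit, treatment-by-visit interaction and time of glargine administration. Visits are repeated within subject with an unstructured covariance, as in the MMRM; a random subject effect is an acceptable alternative. Use this model for both the interaction test and the pooled ratio with its 90% CI. The interaction rule and the by-visit models can stay.

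State the role of Visit 6. Entering its log concentration as a baseline covariate fits SAP 7.2 and the practice in the other models. The within-subject term is the essential correction; the covariate is a sensible addition, and time since last dose is optional.

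The cost is a few words and a different procedure call, with no new data. The downside is a wider interval. Because PK data are locked after the main database, the text can be amended before PK results are available.

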4. STUDY DESIGN

4.1. GENERAL DESCRIPTION

This is a multicenter, double-blind, randomized, parallel-group phase 3 study in patients with type 1 diabetes mellitus (T1DM) comparing the efficacy, immunogenicity and safety of MYL-1501D products from two manufacturing processes (Process V and Process VI). A total of 202 patients with T1DM are planned to be randomized in a 1:1 ratio between MYL-1501D Process V and MYL-1501D Process VI. Approximately 110 sites will be included in the study.

After up to 2-week screening period, all patients will be titrated on Lantus® during a 4-week run-in period, and will be shifted from their current mealtime insulin to Humalog®. The patients will be randomized (stratified by investigational site and time of administration of glargine [morning and evening]); one group will receive MYL-1501D product from Process V, while the other group will receive MYL-1501D product from Process VI for 18 weeks. A follow-up visit will be scheduled 2 weeks after last dose of MYL-1501D.

The none hypothesis is that the upper bound of treatment difference (Process VI minus Process V) is over 0.4 and alternative hypothesis is that upper bound of treatment difference is less than or equal to 0.4.

Patients will remain blinded until the database is locked, then an unblinding request form will be sent to the IVR provider in order to get the randomization code. Any analyses done prior to database lock will use dummy treatments.

Document: \sasdata\Mylan\Insulin_glargine\SYA22825\Biostatistics\Documentation\SAP\MYL-1501D-3004_SAP_Final_2_0_clean.doc

Author: [name]

Version Number:

2.0

Version Date:

18OCT2018

Template No: CS_TP_BS016 Revision 4
Effective Date: 01Apr2016

Reference: CS_WI_BS005

Analysis Plan Template

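### In the exploratory PK analysis a treatment-by-visit significance test decides whether the Process VI/V ratio is reported pooled or by visit; both should always be reported

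*SAP*

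**What the plan says.** SAP V2.0 section 16.3 (Exploratory PK Analysis) starts from a full model: "Treatment group comparison will be done using the GLM model on log-transformed PK concentration values including treatment, visit, treatment-by-visit interaction", together with time of glargine administration, all as fixed effects. Two conditional steps follow.

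- Not significant: "If treatment-by-visit interaction is not significant, this term will be dropped from the model, the reduced model will be performed to produce the final analysis". The reduced model has one treatment effect common to all visits.
- Significant: the arms are compared separately at each visit, adjusting for dosing time alone. The instruction begins "If treatment-by-visit interaction is significant, then this interaction term and visit term will be drop from the model and final model will be performed by".

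On output, "LSMeans for each treatment group and Geometric Mean Ratio between the treatment groups will be calculated", with two-sided 90% intervals and p-values. Whatever the test shows, "Descriptive statistics of PK concentration values will be presented for each scheduled visits by treatment group".

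Section 16.3 sets no level for the interaction test, so the SAP 7.5 default applies: "The default significant level will be (5%); confidence intervals will be 95% and all tests will be two-sided". PK is sampled at Visits 6, 8, 10, 12 and 14. The Visit 6 (Week 0) sample is drawn before study drug, which leaves four post-baseline visits. Section 16.3 does not say whether Visit 6 enters the model.

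**The concern.** The rule makes the reported quantity depend on a test that nobody has sized. If the Process VI/V ratio shifts with exposure, for example by Week 18, and the test does not reach 5%, the shift is averaged with earlier visits that show little or no difference. No ratio or interval for Week 18 is then produced. If the test does reach 5%, the reader gets by-visit ratios but no overall one.

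Other analyses in the same SAP avoid this. The primary HbA1c model (16.1.3) keeps treatment-by-visit and reads the contrast at Week 18. HbA1c by visit, fasting plasma glucose and SMBG (16.2.3) and antibody binding (18.6.1) give treatment differences at each visit with no pre-test. The SAP gives no reason for treating PK differently.

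What is at stake is the completeness of an exploratory result, not a trial decision.

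**Working it through.** **The plan's own figure.** No power is stated for the PK interaction test. The only sample-size calculation is for HbA1c (protocol 7.1): margin 0.4, true difference 0.03, SD 0.74, 90% power. The normal formula gives 85 per arm, and the noncentral t gives the stated 86 per arm (172 in total). 172/0.85 = 202.4, against 202 planned. The number of subjects was therefore fixed by HbA1c alone.

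**Inputs for PK.** "A total of 202 patients with T1DM are planned to be randomized in a 1:1 ratio between MYL-1501D Process V and MYL-1501D Process VI" gives 101 per arm. V = 4 post-baseline visits and alpha = 0.05. The following are assumptions: differences expressed in units of the log-concentration SD, equal correlation between visits of 0 to 0.6, complete data, and the dosing-time term left out of the simulations.

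**Power of the test as written (independent errors).** Noncentrality λ = (n/2) × Σ(d_v − mean d)², with 3 numerator df.

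| Pattern over the 4 visits (SD units) | Σ(d_v − mean d)² | λ at n = 101 | Missed, 101/arm | Missed, 86/arm |
|---|---|---|---|---|
| 0, 0, 0, 0.5 (Week 18 only) | 0.1875 | 9.47 | 26.7% | 34.5% |
| 0, 0.17, 0.33, 0.5 (drift) | 0.1389 | 7.01 | 41.2% | 48.7% |
| 0, 0, 0.5, 0.5 (last two visits) | 0.25 | 12.62 | 14.2% | 20.9% |

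**Correlated samples, same model without a subject term, 101 per arm.** At correlation 0.6 the miss rate is about 25% for Week 18 only and about 50% for drift. The ranges over correlation 0 to 0.6 are therefore about 25-27% and 41-50%.

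**How far the figures move.** SAP 8.2's site pools add up to 219 subjects; at that N and zero correlation the miss rates are 22.9% (Week 18 only) and 37.3% (drift). Over all settings examined at alpha 0.05 (four or five visits, N = 172 to 219, correlation 0 to 0.7) the range is about 2% to 73%. The low end is 0.5 SD at three of five visits with N = 219 and correlation 0.7. The high end is drift over five visits with N = 172 and correlation 0.7.

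**What is reported after a miss.**
- The pooled estimate targets the average: 0.5/4 = 0.125 SD for Week 18 only, and 0.25 SD for drift.
- Its 90% half-width from the fixed-effects model is 1.6468 × √(2/(4 × 101)) = 0.116 SD.
- To contain 0.5 SD the estimate must reach 0.5 − 0.116 = 0.384 SD. With independent samples its standard error is √(2/404) = 0.070. The drift pattern then needs a deviation of (0.384 − 0.25)/0.070 = 1.9 standard errors, about 3%. The Week 18 pattern needs (0.384 − 0.125)/0.070 = 3.7, essentially never.
- Simulating the two-stage rule over correlation 0 to 0.6, the interval contained the Week 18 difference in at most about 1% of missed trials (Week 18 only) and 3-14% (drift).

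**What by-visit reporting would give.** Each visit's 90% half-width is 1.6449 × √(2/101) = 0.23 SD. A 0.5-SD difference at one visit yields a 90% CI excluding no difference in 97.2% of trials at 101 per arm (94.9% at 86). The interaction test detects the same difference in 73% (66% at 86).

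**The case against.** Much of the other side stands.

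- **Exploratory status.** PK is not among the listed objectives or endpoints, there is no PK margin or success rule, and the protocol synopsis attributes PK/PD equivalence of the two processes to earlier work. Samples are single draws, only preferably pre-dose. Nothing in the trial's conclusion rests on the pooled ratio.
- **By-visit descriptives.** These are planned regardless, so a Week 18 separation would be visible, though without a ratio or interval.
- **Pre-specification.** Fixing the reduction rule in advance at least prevents choosing the model after seeing the data.

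Two stronger readings are tempting, and neither is supported. A reader might infer that the SAP takes a non-significant test as proof that the ratio is constant. It states no such conclusion; 16.3 is a model-reduction rule. A reader might also infer that selecting by pre-test ruins the pooled interval's 90% coverage. In a balanced layout the pooled contrast is orthogonal to the interaction contrasts. In simulation with independent samples, coverage of the visit-averaged difference given a non-significant test stayed at about 90%. With correlation 0.3 or 0.6 it fell to about 77% or 67%, but by about the same amount with and without the pre-test. That loss comes from the absence of a subject term, which is a separate matter.

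**Conclusion.** The point holds as a reporting weakness in an exploratory analysis. A test without planned power decides whether the reader sees a pooled ratio or by-visit ratios, and never guarantees both. Under the illustrative assumptions, a 0.5-SD visit-dependent difference goes undetected in about 25-27% (Week 18 only) or 41-50% (drift) of trials, and in about 14% if it is present at two of four visits with independent samples. These rates are not a property of the plan: they depend on the assumed effect size, pattern, N, alpha and correlation. After a miss the pooled interval says little about Week 18, although as far as the pre-test is concerned it remains a valid estimate of the visit average. The primary HbA1c conclusion is untouched, and the change is desirable rather than essential.

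**What to change.** In SAP 16.3 delete both conditional steps and keep treatment-by-visit in the model. From that one model always report:

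- the Process VI/V geometric mean ratio with 90% CI at each post-baseline visit, including Week 18;
- the ratio averaged over the post-baseline visits, with 90% CI.

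Show the interaction p-value for description only.

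The cost is SAP wording and a few more table rows, with no new data. Four samples from 202 subjects give 808 observations. Keeping the interaction leaves 799 error degrees of freedom instead of 802, and the t multiplier is 1.6468 either way, so the averaged ratio keeps essentially the same precision. SAP 16.3 says the PK data are locked after the main database and analysed by the method specified there, so the wording should be changed before that analysis.
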